8.5.5. Pregnancy

Details of all pregnancies in female participants and, if indicated, female partners of male participants will be collected from signing of the study-specific ICF onwards until the last study assessment as outlined in the SoE. If a pregnancy is reported, the PI/investigator should inform the sponsor within 24 hours of learning of the pregnancy and should follow the procedures outlined in [Appendix 3](#), Adverse Events: Definitions and Procedures for Recording, Evaluating, Follow-up, and Reporting.

Abnormal pregnancy outcomes (e.g., spontaneous abortion, foetal distress, foetal death, stillbirth, congenital anomaly/birth defect, ectopic pregnancy) are considered SAEs.

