Pregnancy and birth control	
No reproductive system studies have been conducted with RV299 to date.
 
Drugs or other substances known to be substrates for CYP3A4 or inhibitors of aldehyde oxidase (AO), PgP or breast cancer resistance protein (BCRP) may interact with RV299, which has shown in vitro evidence of being a CYP3A4 inhibitor and an AO, PgP, and BCRP substrate. Caution should be applied in co-administering such therapies, including monitoring for toxicity or subtherapeutic effects.
	
 1) Specific contraceptive requirements will be in place for participants. 2) Contraceptive guidance will be used in inclusion criteria. 3) Female participants will need evidence of negative pregnancy tests prior to dosing.

Potential Risk of Clinical Significance	Description of Risk	Mitigation Strategy
	In particular, female participants who are on hormonal contraception or hormonal replacement therapy that contains oestradiol or ethinyl-oestradiol (both of which are substrates of CYP3A4) should require their male partners to use additional barrier contraceptive methods such as condoms with spermicide during RV299 administration and for at least one menstrual cycle after a course of RV299.	
Study procedures		
Blood Sampling (venepuncture or via a peripheral venous catheter)	Pain or bruising at the site where blood is drawn.	Blood samples will be obtained by a trained professional.
	Syncope (fainting) can occur following or even before any blood draw as a psychogenic response to the needle insertion.	Blood samples will be obtained by a trained professional and procedures will be put in place to avoid injury from fainting.
	There is a possibility that in the process of collecting blood a nerve may be injured.	Procedure to be performed by qualified personnel.
	Blood tests performed to address the health of the participants at screening and during the study may indicate that a participant has an infection that he/she was not previously aware of (such as human immunodeficiency virus [HIV] or hepatitis) or an unexpected illness.	The hVIVO doctor will provide the participant's general practitioner (GP), or doctor with a referral letter if the participant agrees.
Nasal sampling	Collection of respiratory (nasal) samples may cause discomfort, sneezing, watery eyes, irritated nose, or nose bleeding.	Sample collection will be performed by appropriately qualified and trained study staff to minimise the discomfort

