7.	
The following criteria apply to female and male participants:
 
a) Female participants of childbearing potential must use one form of highly effective contraception. Hormonal methods must be in place from at least 14 days prior to the first study visit. The contraception use must continue until 90 days after the last dose of IMP. Highly effective contraception is as described below:
 
 a. Established use of hormonal methods of contraception described below (for a minimum of 14 days prior to the first study visit). When hormonal methods of contraception are used, male partners are required to use a condom with a spermicide: 
 i. combined (oestrogen- and progestogen containing) hormonal contraception associated with inhibition of ovulation: 
 1. oral 2. intravaginal 3. transdermal ii. progestogen-only hormonal contraception associated with inhibition of ovulation: 
 1. oral 2. injectable 3. implantable b. Intrauterine device. c. Intrauterine hormone-releasing system. d. Bilateral tubal ligation. e. Male sterilisation (with the appropriate post vasectomy documentation of the absence of sperm in the ejaculate) where the vasectomised male is the sole partner for that woman. f. True abstinence – sexual abstinence is considered a highly effective method only if defined as refraining from heterosexual intercourse during the entire period of risk associated with the study treatments. The reliability of sexual abstinence needs to be evaluated in relation to the duration of the clinical trial and the preferred and usual lifestyle of the participant. 
b) Male participants must agree to the contraceptive requirements below at entry to quarantine and continuing until 90 days after the last dose of IMP.

No.	hVIVO APPROVED STANDARD INCLUSION CRITERIA (Viral Challenge Volunteer Studies) Final v11.0, 08FEB2022

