	
 a. Use a condom with a spermicide to prevent pregnancy in a female partner or to prevent exposure of any partner (male or female) to the IMP. b. Male sterilisation with the appropriate post vasectomy documentation of the absence of sperm in the ejaculate (please note that the use of condom with spermicide will still be required to prevent partner exposure). This applies only to males participating in the study. c. In addition, for female partners of childbearing potential, that partner must use another form of contraception such as one of the highly effective methods mentioned above for female participants. d. True abstinence – sexual abstinence is considered a highly effective method only if defined as refraining from heterosexual intercourse during the entire period of risk associated with the study treatments. The reliability of sexual abstinence needs to be evaluated in relation to the duration of the clinical study and the preferred and usual lifestyle of the participant. 
c) In addition to the contraceptive requirements above, male participants must have agreed not to donate sperm following discharge from quarantine until 90 days after the last dose of IMP.

8.	Sero-suitable for the challenge virus 
 • The serology result obtained from the RSV-A Memphis 37b virus antibody assay suggests that the participant is sensitive to RSV-A Memphis 37b virus infection (i.e., they are likely to be infected following inoculation with the challenge virus).

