7.5. Stopping Rules

The PI/investigator and the SME will perform safety reviews on available clinical and virology data as appropriate during the quarantine period.

Three clinical scenarios relating to the incidence of SAEs/suspected unexpected serious adverse reactions (SUSARs) during the study and the procedures that should be performed in each case are presented in [Table 7-1](#).

Table 7-1: Study Stopping Rules

Status	Criterion	Procedure
1	A report has been received of one (or more) SUSAR(s) in any, one (or more) participant(s).	If such a status occurs at any point during the study, then further administration of the IMP will not take place. The PI/investigator and the SME will review the data and decide on whether it is appropriate to recommence IMP dosing (approval of a substantial amendment from the Competent Authorities is required) or terminate the study.
2	No SUSAR(s) have been reported but an overall pattern of clinical changes or symptoms exists, attributed to the IMP, which may appear minor or moderate in terms of individual AEs or SAEs, but which collectively represent a concern for safety.	If such a status occurs at any point during the study, then further administration of IMP will not take place. The PI/investigator and the SME will review the data and decide on whether it is appropriate to recommence IMP dosing (approval of a substantial amendment from the Competent Authorities is required) or terminate the study.
3	Unexpected virus-related SAE(s) or unexpected virus-related AE(s) of clinical concern have been reported following viral challenge.	If such a status occurs at any point during the study, then the PI/investigator and the SME will review the data and decide based on expectedness* of the viral event. If the event is unexpected, further administration of the virus will not take place. The PI/investigator and the SME will review the data and decide on whether it is appropriate to recommence inoculation (approval of a substantial amendment from the Competent Authorities is required) or terminate the study.

* Expectedness will be assessed by referring to the challenge virus dossier.

A final follow-up visit will be performed on Day 28 (± 3 days). Follow-up of any event should continue until resolution, stabilisation, it is judged by the PI/investigator to be no longer clinically significant, the participant is lost to follow-up, or an alternative explanation has been provided.

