10.3.11. Pregnancy

If a female participant or female partner of a male participant becomes pregnant during of the study, this must be reported by the PI/investigator to the SME and study monitor by telephone as soon as possible, in accordance with hVIVO SOPs, and at the latest within 24 hours of becoming aware of the event.

Following the telephone notification, the PI/investigator must fully and accurately complete the appropriate pregnancy reporting form, which must be emailed to the SME and the study monitor at the latest within 24 hours of becoming aware of the pregnancy.

Participants will be advised to contact their GP or a specialist, as appropriate.

Consent for follow-up of the pregnancy and pregnancy outcome will be sought from the pregnant study participant or the pregnant partner of the male study participant as applicable. Consent for follow-up will be documented on an hVIVO Pregnancy Follow-up ICF.

Provided that the appropriate consent is in place, information related to the pregnancy will be collected as per hVIVO SOPs and the sponsor's requirements. The completed reporting form(s) will be sent to the sponsor for review and assessment, and subsequent reporting as required.

- A complete evaluation will be documented in the source data to permit transfer to the clinical database.
- The emergency code break envelopes will be requested ([Section 6.3](#), Randomisation and Blinding) to break the blind for the appropriate study participant to ensure that further care can be based on the actual identity of the study intervention that the participant received.
- hVIVO will maintain contact with the participant for a protracted period, but certainly until after the birth, in order to assess for outcomes that may be reportable as related AEs, and for reporting to the sponsor as appropriate.
- hVIVO, in consultation with the participant, will keep the participant's GP informed.
- All cases of foetal drug exposure via the parent as a study participant will be reported to the sponsor and the REC.
- Abnormal pregnancy outcomes (e.g., spontaneous abortion, foetal distress, foetal death, stillbirth, congenital anomaly/birth defect, ectopic pregnancy) are considered SAEs.

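### Planned pregnancy collection stops at the Day 28 visit, although contraception is required until 90 days after the last dose, so 77% to 80% of that period has no planned collection

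*Protocol*

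**What the plan says.** Protocol Section 8.5.5 sets the collection period: details of pregnancies "will be collected from signing of the study-specific ICF onwards until the last study assessment as outlined in the SoE". Section 7.5 and the Schedule of Events (SoE) place the last assessment: "A final follow-up visit will be performed on Day 28", with a window of ±3 days. No later contact is scheduled.

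Inclusion criterion 7 (Section 5.1) sets a longer period for avoiding conception. For women of childbearing potential: "The contraception use must continue until 90 days after the last dose of IMP". For men: "Male participants must agree to the contraceptive requirements below at entry to quarantine and continuing until 90 days after the last dose of IMP". In addition, "male participants must have agreed not to donate sperm following discharge from quarantine until 90 days after the last dose of IMP". The criterion's abstinence items also speak of "refraining from heterosexual intercourse during the entire period of risk associated with the study treatments".

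Appendix 3, Section 10.3.11, sets the reporting duty. Its trigger is "If a female participant or female partner of a male participant becomes pregnant during of the study", with no day or interval given. Once a pregnancy is reported and consent is in place, that section follows it at least until after the birth.

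On the hazard itself, Table 2-1 states: "No reproductive system studies have been conducted with RV299 to date".

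**The concern.** Participants are asked to avoid conception for 90 days after the last dose, but the planned collection of pregnancies covers only the first few weeks of that time. Neither document gives a reason for the shorter period.

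A conception on Day 60, for example, would fall inside the contraception period for every permitted dosing start, but after the last assessment named in Section 8.5.5. The follow-up to birth in Section 10.3.11 does not help unless the pregnancy reaches the site in the first place. Partners of male participants have no scheduled test, so their pregnancies come to light only if someone reports them.

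What is at stake is safety information, not efficacy or the analysis. RV299 has no reproductive studies, and Section 8.5.5 itself classes abnormal pregnancy outcomes as SAEs. Each exposed pregnancy would therefore be informative, however few there are.

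**Working it through.** The documents give no figure for the uncovered share, so there is none to reproduce. The check is calendar arithmetic.

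**Inputs**
- Ten doses about 12 hours apart (SoE note k; Table 6-1).
- Earliest first dose: evening of Day 2. Latest: evening of Day 5 (SoE note k; Synopsis).
- Contraception period: 90 days after the last dose (inclusion criterion 7).
- End of planned collection: Day 28, with a visit window of Day 25 to Day 31 (Sections 8.5.5 and 7.5).

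**Last dose** = first dose + 9 × 12 h = first dose + 4.5 days.
- Start on Day 2 evening: last dose on Day 7 morning.
- Start on Day 5 evening: last dose on Day 10 morning.

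**End of the 90 days** = last dose + 90.
- 7 + 90 = Day 97.
- 10 + 90 = Day 100.

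**Days without planned collection** = end of the 90 days − final visit day; share = days / 90.

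| Final visit | Last dose Day 7 | Last dose Day 10 |
|---|---|---|
| Day 25 | 97 − 25 = 72 (80.0%) | 100 − 25 = 75 (83.3%) |
| Day 28 | 97 − 28 = 69 (76.7%) | 100 − 28 = 72 (80.0%) |
| Day 31 | 97 − 31 = 66 (73.3%) | 100 − 31 = 69 (76.7%) |

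**Change of denominator.** Counting from the first dose makes the period 90 + 4.5 = 94.5 days. The Day 28 share is then 69 / 94.5 = 73.0% to 72 / 94.5 = 76.2%. The result does not depend much on where counting starts.

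**Check of the dosing timeline.** A Day 4 morning start puts dose 10 on Day 8 evening, and 96 hours later is Day 12 evening. It is the earliest start for which that sample falls after Day 12 morning, which agrees with SoE note e. Day 5 evening to Day 12 morning is 6.5 days with 14 assessments, as SAP Section 10.7.1.2 states.

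**The case against.** The strongest reply is that the site is not released from every duty after Day 28. Four provisions support it.

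- The next sentence of Section 8.5.5 requires the sponsor to be told within 24 hours of the investigator learning of a reported pregnancy, and gives no end date.
- Section 10.3.11 requires all foetal drug exposure through a participating parent to be reported to the sponsor and the ethics committee, also undated. It sits under the trigger for pregnancies during the study, so its reach is arguable.
- Section 8.5.1 requires notification of related SAEs learned of at any time after discharge, and abnormal pregnancy outcomes are SAEs.
- The period in Section 10.3.11 could be read up to the end of the study, which the Synopsis defines as the last participant's last visit. In a clinical phase of about 7 months, that would lengthen the period for those enrolled early.

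All of this stands as far as it goes. A reader might infer from Section 8.5.5 that the site has no duty to report or follow a later pregnancy; the documents do not support that. But none of these provisions plans any collection after Day 28. The first three depend on the site happening to hear of a case, and an ordinary ongoing pregnancy is not an SAE. The fourth would still leave the last participants at Day 28, and it does not clearly match Section 8.5.5.

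Three further points are fair. Few pregnancies are likely: 80 participants are planned, 40 of them on placebo, with highly effective contraception required. The interaction warning in Table 2-1 concerns products containing oestradiol or ethinyl-oestradiol and asks for extra barrier methods for at least one menstrual cycle after the course, so it does not establish a 90-day interaction risk. Finally, the consent pages, site procedures and Safety Management Plan were not available, and may already tell participants to report later pregnancies.

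**Conclusion.** The mismatch is real. Section 8.5.5 plans collection to Day 28, while inclusion criterion 7 runs to between Day 97 and Day 100. That leaves 69 to 72 of the 90 post-dose days (77% to 80%) without planned collection, or 66 to 75 days (73% to 83%) with the visit window. Section 10.3.11 leaves its period undefined and needs to be reconciled with Section 8.5.5.

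These figures assume that all ten doses are given on schedule and that collection ends at the final visit, as Section 8.5.5 states. They are shares of calendar days, not of pregnancies. A reader might infer that most pregnancies in the 90 days would never reach the sponsor. The documents do not support that: passive routes exist, voluntary reports could arrive, and neither the sex split nor any expected number of pregnancies is given. The number missed cannot be estimated and is probably small.

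The gap does not affect the efficacy analysis or the validity of the trial. It is a safety-collection rule that stops too early for a drug with no reproductive studies, and it should be corrected because correction is cheap.

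**What to change.** Reconcile Sections 8.5.5 and 10.3.11 with inclusion criterion 7. State in both that pregnancies in female participants and in partners of male participants are collected until 90 days after the last dose of IMP, and are reported within 24 hours of the site becoming aware of them. At the Day 28 visit, instruct participants to report any pregnancy, their own or a partner's, until that date. If the participant information already says this, only the protocol text needs to change.

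No added visit or test is needed, and the contraception requirements stay as they are. The cost is amendment wording and, if needed, a sentence in the participant information. The downside is that the site must keep a passive reporting route open for about 10 weeks after each participant's last visit (69 / 7 = 9.9 to 72 / 7 = 10.3 weeks from Day 28).

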8.6. Pharmacokinetics

Blood samples will be collected for measurement of plasma concentrations of RV299 as specified in the SoE. RV299 concentrations in nasal washes may be explored.

Further to emerging data on RV299, additional blood samples (within the blood volume limit) may be collected at additional time points during the study, if warranted and agreed upon between the PI/investigator and the sponsor. The timing of sampling may be altered during the study based on newly available data (e.g., to obtain data closer to the time of peak plasma concentrations) to ensure appropriate monitoring.

Instructions for the collection and handling of biological samples will be provided by the sponsor. The actual date and time (24-hour clock time) of each sample will be recorded.

Samples will be used to evaluate the PK of RV299. Samples collected for analyses of RV299 plasma concentration may also be used to evaluate safety or efficacy aspects related to concerns arising during or after the study. Genetic analyses will not be performed on these plasma samples. Participant confidentiality will be maintained.

Drug concentration information that may unblind the study will not be reported to investigative sites or blinded study staff until the study has been unblinded.

8.6.1. Pharmacokinetic Blood Samples

Blood samples for the evaluation of PK parameters of RV299 will be collected according to the SoE, and processed and sent to the sponsor's PK vendor according to the AP.

8.6.2. Pharmacokinetic Parameters

Pharmacokinetic parameters of interest may include:

AUC_{τ} , AUC_{0-24h} , $AUC_{0-\infty}$, C_{max} , t_{max} , $t_{1/2}$

Pharmacokinetic parameters will be calculated using non-compartmental methods. Parameters will be summarised descriptively.

CCI

CC

Confidential

Page 72 of 109

9. Statistical Considerations

9.1. Statistical Hypotheses

The primary statistical hypothesis is that treatment with RV299 will show an antiviral effect demonstrated by a significant reduction in RSV viral load AUC (measured by qRT-PCR) compared to placebo.

CCI

9.3. Populations for Analyses

The following populations are defined in [Table 9-1](#).

Table 9-1: Study Populations

Population	Description
Intent-to-treat (ITT) analysis population	All randomised participants who received challenge virus and at least 1 dose of IMP
Intent-to-treat infected (ITT-I) analysis population	All randomised participants who received challenge virus and at least 1 dose of IMP, and meet the criterion for laboratory-confirmed RSV infection
Intent-to-treat infected analysis population A (ITT-A)	All randomised participants who received challenge virus and at least 1 dose of IMP and meet the criterion for laboratory-confirmed RSV infection using only assessments prior to taking IMP
Intent-to-treat infected analysis population B (ITT-B)	All randomised participants who received challenge virus and at least 1 dose of IMP and meet the criterion for laboratory-confirmed RSV infection using only assessments after taking IMP
Per protocol (PP) analysis population	All ITT-I analysis population participants who have no major protocol deviations, and who completed the quarantine period up to the final day of quarantine (Day 12) and received all 10 doses of IMP

Population	Description
Safety analysis population	All randomised participants who received challenge virus and at least 1 dose of IMP
PK analysis population	All ITT analysis population participants with at least one post-dose PK result

Membership of participants in each analysis set will be determined at a planned blinded data review meeting, prior to any analysis and database lock.

The primary efficacy analysis population will be on the ITT-I analysis population, and the ITT-A, ITT-B, and PP analysis populations will be used for sensitivity analysis, as defined in the statistical analysis plan (SAP). The safety evaluation will be performed on the safety analysis population. Additional analysis sets may be defined in the SAP.

9.4. Statistical Analyses

This section is a summary of the planned statistical analyses of the most important endpoints including primary and key secondary endpoints.

Data will be analysed and reported using SAS® version 9.4 or later.

CC1

9.4.1. Statistical Analysis Plan

The SAP will be developed and finalised prior to database lock for the study. The finalised SAP will be signed prior to unblinding the study data. Full details of the planned statistical analysis will be presented in the SAP that will include a more technical and detailed description of the statistical analyses described in the current protocol section.

Any deviation(s) from the original statistical plan outlined in the protocol will be described and justified in an amendment to the protocol and/or SAP, as appropriate, and referenced in the final clinical study report (CSR).

CC1

